1.8 Primary Specimen Collection

N/A

1.9 Interviews, Focus Groups, or Surveys

A. Administration

The Clinical COPD Questionnaire (CCQ) will be administered by research staff during a telephone interview at 30 days following subject enrollment into the study. The patient will be provided this document in advance, at the time of hospital discharge, for reference.

B. Study Instruments

The CCQ is a validated tool utilized in prior literature to assess quality of life in patients with COPD. Higher scores indicate increased severity of symptoms and/or poorer quality of life, and are associated with increased mortality. ^{17, 18, 19, 20, 21}

In addition to the CCQ, research staff will query the patient about study endpoints during the follow-up telephone interview (re-admission, changes to steroid regimen, antibiotic therapy, and steroid-associated adverse effects that require a consultation, an invasive procedure, or initiation of a specific therapy).

1.10 Timetable/Schedule of Events

Patients will be enrolled and followed for a total of 30 days. If follow-up is still unable to be obtained 14 days after the 30-day follow-up date, the patient will be considered lost to follow-up. The global timetable for the study is unknown, as the volume of patient recruitment is unclear.

Protocol Number:

PI Name: [name]

Protocol Title: Determining Optimal Dose of
Corticosteroids in COPD Exacerbations: A
Pilot Study

7

RESERVED FOR IRB STAMP
DO NOT MODIFY THIS SPACE

IRB Form Version v120116

2.2 Resources Available

The study will utilize locked file cabinets and a password protected workstation in the GIM office, CAB suite 2300. [name] will keep the key for the file cabinet.

All research co-investigators undergo initial two-hour training sessions regarding study protocol, procedures, and duties. On-going research procedures are supervised by [name] and the data analyst to ensure protocol compliance.

2.3 Research Sites

Robert Wood Johnson University Hospital

3.0 Multi-Site Research Communication & Coordination

N/A

3.1 Outside Research

N/A

Protocol Number:

PI Name: [name]

Protocol Title: Determining Optimal Dose of
Corticosteroids in COPD Exacerbations: A
Pilot Study

8

RESERVED FOR IRB STAMP
DO NOT MODIFY THIS SPACE

IRB Form Version v120116

4.0 Research Data Source/s

4.1 Primary Data-Subjects and Specimens

Thirty day follow is obtained from patient/proxy via telephone contact (see data collection form).

4.2 Subject Selection and Enrollment Considerations

A. Recruitment Details

Emergency room and medical staff will be informed about the study objectives, eligibility criteria, and protocol requirements prior to the initiation of the study. We will only recruit patients of physicians who are willing to follow the study protocol. Study staff will be notified of potential subjects that are identified by the emergency room staff and physicians. Study staff can also access a list of patients in the hospital who are being treated with prednisone or methylprednisolone to identify additional potential study subjects. Study staff will assess the medical records of each of the potential study subjects and, if they meet all eligibility criteria, approach the patient for consent. Eligible patients would have a diagnosis of COPD, emphysema, or chronic bronchitis with a presentation of increased dyspnea, increased sputum, or increased cough.

B. Source of Subjects

Subjects will be recruited from the RWJUH emergency room and general medical ward.

C. Method to Identify Potential Subjects

See section A above.

D. Subject Screening

Individuals will be screened for study inclusion by study staff using the eligibility and screening form.

▪ Inclusion Criteria

- Patients with a diagnosis of COPD, emphysema, or chronic bronchitis
- Age \geq 40 years-old
- Smoking history \geq 10 pack-years
- Presentation to the emergency room with increased dyspnea, increased sputum, or increased cough
- Admission to the hospital

▪ Exclusion Criteria

- Alternative diagnosis for cause of dyspnea, increased sputum or cough
- Patients who require intubation at time of recruitment
- Patients who are unable to give consent
- Patients who are pregnant or could be pregnant or are currently breast-feeding

Protocol Number:

PI Name: [name]

Protocol Title: Determining Optimal Dose of
Corticosteroids in COPD Exacerbations: A
Pilot Study

9

RESERVED FOR IRB STAMP
DO NOT MODIFY THIS SPACE

IRB Form Version v120116

- Women of child-bearing age who cannot use methods of contraception as described in the consent, including condoms, female condoms, cervical caps, diaphragms, and IUDs.
- Patients who were previously entered into the trial and are re-admitted to the hospital with a new COPD exacerbation.

A younger population is excluded because COPD is primarily an adult disease.

E. Recruitment Materials

Subjects will be given a copy of the informed consent as well as a short patient brochure describing the salient points of the study.

F. Lead Site Recruitment Methods

N/A

4.3 Subject Randomization

At the time of recruitment, subjects are assigned a consecutively numbered patient identifier by the study staff. This patient identifier is communicated to the research pharmacy. The research pharmacy then assigns a separate randomization identifier based on a previously computer generated randomization chart. The randomization identifier is communicated back to the study staff. This randomization identifier is associated with a specific treatment arm (low-dose or high-dose) on the randomization chart. The treatment arm associated with the randomization identifier **is not communicated** to the research staff because this is a double-blinded study. Study drug is prepared by the research pharmacy based on the assigned treatment arm.

4.4 Secondary Subjects

N/A

4.5 Number of Subjects

- A. Total Number of Subjects:** 125
- B. Total Number of Subjects If Multicenter Study:** N/A
- C. Require Number of Subjects to Complete Research:** This is a pilot study and our goal is to recruit as close to 125 subjects as possible.
- D. Feasibility Of Recruiting:** COPD exacerbation is a common reason for inpatient admission, however recruiting may be limited to unquantifiable external factors (ie. patient interest, physician participation, etc.).

4.6 Consent Procedures

A. Consent

- **Documenting Consent**

Protocol Number:

PI Name: [name]

Protocol Title: Determining Optimal Dose of
Corticosteroids in COPD Exacerbations: A
Pilot Study

10

RESERVED FOR IRB STAMP
DO NOT MODIFY THIS SPACE

IRB Form Version v120116

Informed consent will be obtained directly from the participant using study informed consent. If the patient agrees to participate in the trial, the signed IRB approved consent form will be placed in the subject's study file and the recruiter will keep make a copy to be placed in the patient's medical record and a copy to provide to the participant.

▪ **Waiver of Documentation Of Consent**

N/A, all consent will be documented.

▪ **Waiver or Alteration of Consent Process**

N/A

B. Consent Process

▪ **Location of Consent Process**

Consent will take place in the patient's hospital room.

▪ **Ongoing Consent**

The patient will be spoken with daily by the study staff while hospitalized to address any patient concerns regarding ongoing consent and potential adverse effects.

▪ **Individual Roles for Researchers Involved in Consent**

1. Consent Discussion Duration

The consent discussion is expected to take an average of 15-30 minutes depending on the level of subject understanding.

2. Coercion or Undue Influence

Vulnerable subjects that are unable to give consent or do not adequately understand the study are excluded from recruitment. Aside from paid-for trial medication, the study does not incentivize subject participation in any way, minimizing undue influence on indigent populations.

3. Subject Understanding

After the study is explained to the subjects, study staff will administer the Evaluation to Sign Consent which will document the subject's understanding of the study protocol. Only who provide acceptable responses to the Evaluation to Sign Consent will be enrolled.

4.7 Special Consent/Populations

A. Minors-Subjects Who Are Not Yet Adults

▪ **Criteria for Consent of Minors**

N/A

▪ **Wards of the State**

Protocol Number:

PI Name: [name]

Protocol Title: Determining Optimal Dose of
Corticosteroids in COPD Exacerbations: A
Pilot Study

11

*RESERVED FOR IRB STAMP
DO NOT MODIFY THIS SPACE*

IRB Form Version v120116

N/A

1. Research in NJ Involving Minors

N/A

2. Research Outside of NJ Involving Minors

N/A

▪ **Parental Permission**

N/A

▪ **Non-Parental Permission**

N/A

▪ **Assent Process**

N/A

1. Documentation of Assent

N/A

▪ **Non-English Speaking Subjects**

Non-English speakers will not be recruited

1. Process for Non-English Speaking Subjects

N/A

▪ **Short Form Consent for Non-English Speakers**

No one will be enrolled using the short form consent

B. Adults Unable to Consent / Cognitively Impaired Adults (*for interventional studies*)

▪ **NJ Law-Assessment of Regaining the Capacity To Consent**

N/A, subjects unable to give consent are excluded from this study.

▪ **Capacity To Consent**

N/A

▪ **NJ Law-Selecting A Witness**

N/A

▪ **Removing a Subject**

N/A

4.8 Economic Burden and/or Compensation for Subjects

A. Expenses

Subjects will not incur any additional expenses as a result of study participation.

B. Compensation/Incentives

Subjects will not be incentivized in any way for participation in the study, with the exception that trial medication will be provided at no cost to the subjects.

4.9 Risks to Subjects

A. Description of Subject Risk

Patients entered into this study would have received corticosteroids regardless of study participation. The optimal dose of corticosteroids in the treatment of COPD exacerbations in patients admitted to the hospital is unknown. The proposed regimen for the low-dose

Protocol Number:

12

PI Name: [name]

Protocol Title: Determining Optimal Dose of
 Corticosteroids in COPD Exacerbations: A
 Pilot Study

*RESERVED FOR IRB STAMP
 DO NOT MODIFY THIS SPACE*

IRB Form Version v120116

corticosteroid group is based on national consensus guidelines, and the regimen for the high-dose group, on current clinical practices. Thus, the risks to subjects from study participation are comparable to current standard of care. Any patient who does not clinically improve appropriately can have their regimen intensified based on the clinical judgement of his/her physician. Additionally, if the treating physician feels that the patient is experiencing undue adverse effects from study corticosteroid, the patient may be withdrawn from the study at any time. Minor side effects (ie. hyperglycemia) from short-term systemic corticosteroids are common and generally limited in duration to the duration of treatment. They are an accepted consequence of the standard of care for COPD exacerbation. Major adverse effects are uncommon.

B. Procedures for Risks to Embryo, Fetus, and/or Pregnant Subjects

N/A, these subjects are excluded from the study.

C. Risks to Non-Subjects

N/A

D. Assessment of Social Behavior Considerations

Temporary psychiatric symptoms or exacerbation of pre-existing psychiatric disease are uncommon but potential side effects of corticosteroid therapy. The duration of these side effects are limited to the duration of corticosteroid therapy. Patients entered into this study would have received corticosteroids regardless of study participation. Thus, study participation is unlikely to increase risk of these side effects.

▪ **Reasonably Foreseeable Risks**

There are no other reasonably foreseeable social behavior risks of participation in this study.

▪ **Risk Of Imposing An Intervention On Subject With Existing Condition**

See above.

▪ **Other Foreseeable Risks**

N/A

▪ **Observation And Sensitive Information**

N/A

E. Minimizing Risks

Strict measures are in place to ensure patient confidentiality. Direct patient identifiers (names, addresses, and telephone numbers) will be collected on a separate form from the clinical data and will be kept in a locked file cabinet in the Department of General Internal Medicine, CAB suite 2300. The identifiers will never be entered into an electronic database. Subjects will be given a sequential study identification number that will be used on all forms that collect clinical data and in the electronic database.

The treatment regimens being compared are commonly used in current clinical care and would have been prescribed for the patients regardless of study participation. If the patient's

Protocol Number:

PI Name: [name]

Protocol Title: Determining Optimal Dose of
Corticosteroids in COPD Exacerbations: A
Pilot Study

13

RESERVED FOR IRB STAMP
DO NOT MODIFY THIS SPACE

IRB Form Version v120116

symptoms are not adequately relieved by the study medication, the treating physician is permitted to administer supplemental steroid as needed.

Patients will be followed while in the hospital (for up to 30 days) and at 30 days following study entry. All serious adverse events that have occurred will be identified and reported to the Institutional Review Board.

Any subject deaths will be reported within 24 hours of identification. Serious events will be defined as any event that is life threatening requires or prolongs hospitalization, produces a disability, results in a congenital anomaly/birth defect, or other conditions which in the judgment of the investigators represent significant hazards. All serious adverse events will be reported within one week of identification. All unexpected events meeting will be reported within two weeks of identification if they meet the following criteria:

Unexpected: not identified in nature, severity or frequency in the current IRB-approved research protocol, the informed consent document, the package insert for a given drug or the investigator's brochure.

Associated with the study intervention: there is a reasonable possibility that the event may have been caused by the research intervention.

F. Certificate of Confidentiality

N/A

G. Potential Benefits to Subjects

There is no direct benefit to study participants.

H. Provisions to Protect the Privacy Interests of Subjects

Subjects will interact with a limited number of study staff, primarily during the initial recruitment/inpatient follow-up period. Any privacy interests will be honored by study staff.

I. Research Team Access To Subject Data

Study participants will be asked to sign a Release of Medical Record form, allowing the research team to access medical information from all subsequent hospitalizations and outpatient physician visits within the 30-day follow up period.

4.10 Secondary Data – Records/Chart Reviews/Databases/Tissue Banks/etc.

4.11 Chart/Record Review Selection

For the index hospitalization, study staff will review the hospital medical record (paper and electronic) at the time of discharge for each outcome. The electronic record system is Sunrise Clinical Manager. Paper data collection forms that contain personal identifiers and health information will be kept locked in a

Protocol Number:

PI Name: [name]

Protocol Title: Determining Optimal Dose of
Corticosteroids in COPD Exacerbations: A
Pilot Study

14

RESERVED FOR IRB STAMP
DO NOT MODIFY THIS SPACE

IRB Form Version v120116

filings cabinet in the Department of General Internal Medicine, CAB suite 2300. Study variables and outcomes will be entered into an electronic database using identification numbers for the study subjects. With the exception of dates, the database will not contain personal identifiers. Only study staff will have access to the paper data collection forms and electronic database. In addition, all electronic data will be password-protected and stored on a HIPAA compliant university computer in the Department of General Internal Medicine. Please see the Data Collection Form for variables that will be collected/analyzed. Any forms linking collected data with patient identifiers will be destroyed at the completion of the study (2 years following termination of patient enrollment).

4.12 Secondary Specimen Collection

N/A

5.0 Special Considerations

5.1 Health Insurance Portability and Accountability Act (HIPAA)

HIPAA data (patient identifiers) will be collected as part of the data collection process. This data will not be disclosed and all patient identifiers will be destroyed at the completion of the study following data analysis. Authorization for study staff to obtain/analyze HIPAA data is included in the consent form.

5.2 Family Educational Rights and Privacy Act (FERPA)

N/A

5.3 NJ Access to Medical Research Act

N/A

5.4 Code of Federal Regulations Title 45 Part 46 (Vulnerable Populations)

A. "Special" Classes Of Subjects

- (1) *Pregnant Women*: N/A, these subjects are excluded from the study.
- (2) *Neonates*: N/A, these subjects are excluded from the study.
- (3) *Neonates of Uncertain Viability*: N/A, these subjects are excluded from the study.
- (4) *Prisoners*: N/A, these subjects are excluded from the study.
- (5) *Children*: N/A, these subjects are excluded from the study.
- (6) *Cognitively Impaired Adults*: N/A, these subjects are excluded from the study.

6.0 Research Data Protection and Reporting

6.1 Data Management and Confidentiality

A. Descriptive statistics (e.g., means, standard deviations, ranges, frequency distributions) will be examined for all relevant measures, and transformations of measures will be considered on the bases of distribution diagnostics and outlier analysis. The baseline characteristics of the patients in each of the two arms of the trial will be described and compared using chi-square statistics for categorical variables and t-tests or Wilcoxon statistics for continuous variables.

Protocol Number:

PI Name: [name]

Protocol Title: Determining Optimal Dose of
Corticosteroids in COPD Exacerbations: A
Pilot Study

15

RESERVED FOR IRB STAMP
DO NOT MODIFY THIS SPACE

IRB Form Version v120116

The intention-to-treat principle will be used for all randomized comparisons of study outcomes. The event rates for the primary, secondary, and tertiary clinical outcomes will be compared according to assigned corticosteroid group using chi-square statistics. The test for differences between groups in the composite primary outcome will be conducted at an alpha level of 0.05. The event rates for the individual clinical events and the additional pre-specified clinical events will be tested by treatment group with an alpha=0.01 to adjust for multiple comparisons. Event rates, absolute differences, and relative risks will be estimated, and 95% confidence intervals will be calculated.

B. This is a pilot study to establish an adequate sample size for a larger scale study as well as baseline event rates, thus a power analysis is not included in this submission.

C. Paper data will be stored in a locked filing cabinet in the Department of General Internal Medicine. A password-protected electronic database (that does not contain patient identifiers) will be stored on a HIPAA-compliant university computer at the same location. [name] will have sole access to this data until the study enters the data analysis phase. All study personnel are already trained in HIPAA procedures and have signed HIPAA confidentiality agreements as part of obtaining access to the Sunrise Clinical Manager system.

D. Collected data will be reviewed for quality and internal consistency by study staff after initial collection and before the data analysis phase of the study.

E. Data to be collected includes patient identifiers and can be found in the data collection form. This data will be stored on paper and in an electronic database as detailed above. Paper data will be transported by research staff involved in patient recruitment/data collection to the central data repository at the General Internal Medicine office. Patient identifying data will be stored for 2 years following termination of patient enrollment (completion of the study), at which point all patient identifiers will be permanently destroyed. De-identified data will be retained indefinitely for future research purposes. All co-investigators will potentially have access to research data for data analysis/quality control purposes. Access to the data is controlled by the study data analyst, who maintains the central repository of paper/electronic data.

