1.5 Sample Size Justification

This is a pilot study of 125 subjects to determine the rates of the outcomes so an adequate sample size can be determined and feasibility established. We do not anticipate including enough patients to have adequate power to definitively answer the hypothesis.

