1.6 Study Variables

A. Independent Variables, Interventions, or Predictor Variables

Our independent variable is the corticosteroid intervention. We chose to compare two commonly used corticosteroid regimens for COPD exacerbation that vary by dosage strength but not duration. Both of these regimens may be considered "standard of care."

B. Dependent Variables or Outcome Measures

- i. Primary Outcome: The composite of treatment failure defined as death, intubation, re-admission for COPD exacerbation, or intensification of therapy (increased steroid use, change of antibiotic therapy) within a 30-day follow-up period.
- ii. Secondary Outcomes: Length of hospital stay and quality of life measured by Clinical COPD Questionnaire. The CCQ consists of 10 questions about the severity of COPD symptoms and limitation of activities over the prior week.
- iii. Tertiary Outcome: Composite outcome of short-term adverse effects. Defined as hyperglycemia, hypertension, adrenal suppression, psychiatric disturbance, infection, and gastrointestinal bleed that require a consultation, an invasive procedure, or initiation of a specific therapy.

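### Section 6.1.A compares both secondary outcomes as event rates by chi-square, but length of stay and CCQ score are numerical and the text supplied defines no event or cut-point for either

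*Combined protocol and SAP*

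**What the plan says.** Sections 1.3 and 1.6 define the secondary outcomes in the same words: "Secondary Outcomes: Length of hospital stay and quality of life measured by Clinical COPD Questionnaire". Section 1.1 frames the two secondary aims as a shorter stay and better quality-of-life scores. Section 1.9 describes the CCQ as a graded score on which higher is worse.

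The between-arm analysis is in section 6.1, paragraph A. For outcomes it says: "The event rates for the primary, secondary, and tertiary clinical outcomes will be compared according to assigned corticosteroid group using chi-square statistics". The effect measures follow: "Event rates, absolute differences, and relative risks will be estimated, and 95% confidence intervals will be calculated".

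Tests for continuous data appear once in that paragraph, in the sentence that begins "The baseline characteristics of the patients in each of the two arms of the trial will be described and compared using chi-square statistics" and goes on to name "t-tests or Wilcoxon statistics for continuous variables". That sentence concerns baseline characteristics. The paragraph opens with a general descriptive plan: "Descriptive statistics (e.g., means, standard deviations, ranges, frequency distributions) will be examined for all relevant measures".

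**The concern.** A chi-square test on event rates needs each patient classed as having or not having an event. Length of stay is a number of days and the CCQ is a score. Taken literally, the rule requires someone to choose a threshold for each, and the plan sets none. If that choice is made after the data are seen, both secondary results depend on it.

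A threshold would also change the question. A relative risk of exceeding some number of days is not an estimate of how much shorter the stay was, and the proportion above some CCQ value is not a difference in scores. The pilot is meant to inform a larger trial ("This is a pilot study of 125 subjects to determine the rates of the outcomes so an adequate sample size can be determined"), yet for these two outcomes the plan names no between-arm difference in natural units and no interval for one.

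**Working it through.** **Text check.** The plan gives no power, effect size, SD or event rate for these outcomes, so there is no figure to reproduce. The question is whether the type of variable matches the method.

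| Outcome | Type | Event or cut-point in the text supplied | Between-arm method in 6.1.A |
|---|---|---|---|
| Primary composite (treatment failure) | Binary | Yes | Chi-square, relative risk: fits |
| Length of stay | Days | None | Chi-square on event rates: does not fit |
| 30-day CCQ | Score | None | Chi-square on event rates: does not fit |
| Tertiary composite (adverse effects) | Binary | Yes | Chi-square, relative risk: fits |

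**Illustration of how much the missing cut-point matters.** Only N = 125 (sections 1.5 and 4.5) comes from the plan. The other inputs are assumptions: 1:1 allocation (n = 62.5 per arm), complete data, roughly normal CCQ scores with SD 1, a true difference of 0.5 SD, and two-sided alpha 0.05. The worse arm is centred at +0.25 and the better arm at −0.25.

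*Step 1. Proportions above a cut c.* Worse arm: 1 − Φ(c − 0.25). Better arm: 1 − Φ(c + 0.25). The pooled 25th, 50th and 75th percentiles are at c = −0.696, 0 and 0.696.

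| Cut | Worse arm above | Better arm above | Risk difference | Relative risk |
|---|---|---|---|---|
| 25th percentile | 82.8% | 67.2% | 15.6 points | 0.67213/0.82787 = 0.81 |
| 50th percentile | 59.9% | 40.1% | 19.7 points | 0.40129/0.59871 = 0.67 |
| 75th percentile | 32.8% | 17.2% | 15.6 points | 0.17213/0.32787 = 0.52 |

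One underlying difference thus gives relative risks from 0.81 to 0.52, according to a threshold the plan does not set.

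*Step 2. False positives if the cut is chosen afterwards.* I simulated 40,000 trials with no true difference, 62 versus 63 patients, and tested at the pooled 25th, 50th and 75th percentiles. With an uncorrected chi-square, at least one of the three cuts gave p<0.05 in 12.4% of trials (single cuts 6.3%, 4.8% and 3.8%); a repeat run gave 12.5%. With Yates' correction the figure is about 8%. Searching five cuts from the 30th to the 70th percentile, uncorrected, gave 14.7%.

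*Step 3. Power, for completeness.*

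- t-test: noncentrality 0.5 × √(62.5/2) = 2.795 on 123 degrees of freedom, critical value 1.979, power 79.2%.
- Median split: power = Φ[(D − 1.96 × SE0)/SE1], where D is the risk difference, SE0 the standard error under no difference (pooled proportion) and SE1 that under the assumed proportions. With D = 0.1974, SE0 = √(2 × 0.5 × 0.5/62.5) = 0.0894 and SE1 = √[(0.599 × 0.401 + 0.401 × 0.599)/62.5] = 0.0877, this is Φ(0.252) = 60.0%.
- Cut at either quartile: the same formula with D = 0.1557, SE0 = 0.0775 and SE1 = 0.0762 gives Φ(0.05) = 52.1%.

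*Step 4. What a numerical analysis would report.* The 95% confidence interval half-width for a mean difference with 62 versus 63 patients is 1.979 × √(1/62 + 1/63) = 0.35 SD.

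**The case against.** The best defence is that the sentence is loose wording and does not signal an intention to dichotomise. Neither outcome has an event rate. The same paragraph plans means and SDs, considers transformations after looking at distributions, and names tests for continuous variables, so the authors may simply have failed to carry those tests over to the outcomes. That is plausible, and it softens the reading of intent. It does not supply a method. If the secondary outcomes are read out of the chi-square sentence, the plan has no between-arm analysis for either secondary aim, and the same repair is needed.

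Other points stand in part:

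- Absolute differences could be meant to cover mean differences. Placed between event rates and relative risks, the phrase more naturally means risk differences.
- The data collection form, cited in sections 1.3 and 4.11, was not supplied and could hold categories. If so, they belong in 6.1.A, and they still would not estimate days or score points.
- The pilot's stated purpose leans on event rates ("This is a pilot study to establish an adequate sample size for a larger scale study as well as baseline event rates"), and SDs are already planned descriptively. The loss for sizing the next trial is therefore modest; the loss for secondary aims (a) and (b) is the larger one.
- The inflated false-positive rate arises only if a cut is actually chosen after the data are seen, and its size depends on the continuity correction, which the plan does not specify.
- Complete CCQ data are unlikely, since death is part of the primary outcome and the plan has a rule for loss to follow-up. The illustration covers a normally distributed score and does not represent length of stay.
- The trial disclaims adequate power, so lost power is not the main harm.

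**Conclusion.** The concern holds and should be fixed. It is a stated rule that does not fit the two outcomes it names, which is more than a missing detail. The mismatch is established from the text alone and needs no numerical assumption; its one limit is that the data collection form was not available. The consequences are an unset cut-point for both secondary outcomes and no planned estimate of the quantities that secondary aims (a) and (b) concern.

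The relative-risk spread and the false-positive rates show scale only. They rest on normal scores, 1:1 allocation and 125 complete patients, with the 0.5 SD difference applying to the relative risks and the condition of no true difference applying to the false-positive rates. Seriousness is moderate, because the primary and tertiary analyses are untouched and the study does not claim a definitive answer.

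**What to change.** Amend section 6.1, paragraph A, before the data are analysed:

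1. Limit chi-square tests, risk differences and relative risks to the binary outcomes: the primary and tertiary composites and their components.
2. Compare length of stay by the Wilcoxon rank-sum test, with a location or median difference and its 95% confidence interval.
3. Compare 30-day CCQ by t-test or Wilcoxon, with a mean or median difference and its 95% confidence interval. Say which test, or by what rule it will be chosen.
4. Report summaries of both outcomes by arm.
5. If a binary version of either is also wanted, write its cut-point into the plan.

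While editing, state how deaths enter each analysis, since an in-hospital death shortens the stay and leaves no CCQ. State also which alpha applies: the paragraph gives 0.05 for the primary composite and 0.01 for individual and additional clinical events, and names neither of these outcomes. Another method for numerical data would also serve, provided it is named in advance and yields a difference with an interval.

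The cost is a few sentences of analysis wording. No new data or patients are needed.
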